4. TREATMENTS

4.1 INVESTIGATIONAL TREATMENTS

Patients will receive xentuzumab plus abemaciclib.

Additionally in cohorts B, C, D (dose finding), F, D1 and D2, patients will receive in addition background hormonal therapy with letrozole, anastrozole or fulvestrant.

The sources for each of the products are listed in [Section 4.1.1](#).

As of 19 Oct 2021, based on the primary analysis of top line results of 1280-0022, Boehringer Ingelheim recommended to immediately discontinue xentuzumab in 1280.18 trial. (see [Section 2.3](#))

4.1.1 Identity of the Investigational Medicinal Products

Table 4.1.1: 1 Xentuzumab (Investigational product, IMP)

Substance:	Xentuzumab humanized monoclonal antibody
Pharmaceutical formulation:	Concentrate for solution for infusion
Source:	Boehringer Ingelheim Pharma GmbH & Co. KG
Unit strength:	10 mg/ml of xentuzumab supplied in 20 ml vials (200 mg/vial)
Posology	Once weekly administrated through one hour intravenous infusion. Infusion duration may be extended to over one hour and up to a maximum of three hours in cases of grade ≥ 2 infusion reactions
Route of administration:	Intravenous infusion. Appropriate dose of xentuzumab will be diluted in isotonic sodium chloride solution (0.9%)
Duration of use:	Continuous weekly dosing (days 1, 8, 15 and 22 in a 28-day course) in the absence of disease progression, intolerable AEs or other reason necessitating withdrawal

Detailed preparation and handling of xentuzumab, including information on infusion equipment and infusion procedure, will be described in ISF.

Table 4.1.1: 2 Abemaciclib (Investigational product, IMP)

Substance:	Abemaciclib. Small molecule CDK4 and CDK6 inhibitor
Pharmaceutical formulation:	Capsules
Source:	[REDACTED]
Unit strength:	A white hypromellose capsule containing 50 mg of abemaciclib and the inactive ingredients pregelatinized starch, dimethicone, and colloidal silicon dioxide.
Posology	Treatment/28-day cycle 150 mg p.o. Q12H on Days 1-28 (Starting dose Cohort A) Abbreviations: PO = orally; Q12H = every 12 (\pm 2) hours
Route of administration:	p.o.
Pharmaceutical formulation:	Tablets
Source:	[REDACTED]
Unit strength:	Film-coated 50 mg tablets
Posology	Treatment/28-day cycle 150 mg p.o. Q12H on Days 1-28 (Starting dose Cohort A) Abbreviations: PO = orally; Q12H = every 12 (\pm 2) hours
Route of administration:	p.o.

Table 4.1.1: 3 Fulvestrant. Background endocrine therapy. (Auxiliary Medicinal Product, AMP)

Substance:	Fulvestrant (Faslodex®)
Pharmaceutical formulation:	Solution for injection
Source:	[REDACTED]
Unit strength:	Prefilled syringes (250 mg fulvestrant in 5mL solution).
Route of administration:	Intramuscular injection

Table 4.1.1: 3 (cont.) Fulvestrant. Background endocrine therapy. (Auxiliary Medicinal Product, AMP):

Substance:	Fulvestrant (Faslodex®)
Posology	500 mg given once a month, with an additional 500-mg dose given two weeks after the first dose. Each dose is given as two slow 250 mg injections lasting one to two minutes, with one injection being given into the muscle of each buttock
Route of administration:	Intramuscular injection

Table 4.1.1: 4 Anastrozole. Background endocrine therapy. (Auxiliary Medicinal Product, AMP)

Substance:	Anastrozole
Pharmaceutical formulation:	Film Coated Tablet
Source:	EU, US or Japan commercial product as applicable
Unit strength:	1 mg
Posology	1 mg tablet once a day
Route of administration:	p.o.

Table 4.1.1: 5 Letrozole. Background endocrine therapy. (Auxiliary Medicinal Product, AMP)

Substance:	Letrozole
Pharmaceutical formulation:	Film coated tablet.
Source:	EU, US or Japan commercial product as applicable
Unit strength:	2.5 mg
Posology	2.5 mg once daily
Route of administration:	p.o.

4.1.2 Selection of doses in the trial

4.1.2.1 Part 1

A semi-mechanistic PK/PD model was developed describing the kinetics of the interaction between xentuzumab and the different PD biomarkers (i.e. IGF-1, IGF-2, and IGFBP3). Simulations using this model indicate that a weekly dosing of 1000 mg xentuzumab reduces free IGF-1 concentration by more than 90% and in addition free IGF-2 by 64 % at trough steady-state relative to pre-treatment; this is considered a relevant biological effect. Therefore, a weekly dose of 1000 mg xentuzumab is considered a suitable dose.

In dose finding cohort A, the starting dose of abemaciclib is 150 mg every 12 (± 2) hours. Based on the recommended phase II dose in one dose finding study using combination of a targeted therapy agent with xentuzumab (please refer to the current version of the Investigator's Brochure, [c01690707-08](#)), a dose level of 1000 mg with weekly dose schedule is selected as the starting dose for this study. This dose combination has a prior probability of overdosing below 25% (see [Section 7.1](#)). Planned dose levels for patients in cohort A are displayed in [Table 4.1.2.1: 1](#) below.

Table 4.1.2.1: 1 Concomitant dosing schedule schemes of Cohort A

Dose level	Xentuzumab (mg weekly)	Abemaciclib (mg/12h)
DL0 (starting dose)	1000	150
DL-1a	750	150
DL-1b	1000	100

Dose escalation beyond the highest dose levels planned as shown above will not be considered. Above dose levels may be modified and/or additional dose levels/administration regimens may be added based on safety profile and other emerging data upon discussion and agreement between the sponsor and the SC.

Intra-patient dose escalation is not permitted. Successive dose-level cohorts of patients will receive doses of xentuzumab in combination with abemaciclib until the MTD₁/RP2D₁ is established or until the trial is terminated for other reasons (see [Section 3.3.4.2](#)). The trial may be terminated at any time based on emerging safety concerns without establishing the MTD₁/RP2D₁.

For any dose-level cohort, at least 3 evaluable patients will be required. However, in the case that only 2 patients are evaluable and neither has experienced a DLT within the MTD evaluation period, then dose-escalation can occur based on these 2 patients.

If DLTs are observed in the first two consecutive patients of a previously untested dose level, subsequent enrolment to that dose-level cohort will be stopped. The BLRM will then be re-run to confirm that the dose level still fulfils the EWOC principle. Based on this information, the SC will evaluate whether the next patients will be enrolled at the same dose level, or if they will be enrolled at a lower dose level.

After all patients in the initial dose-level cohort have either experienced a DLT or have been observed for at least one course (28 days) without experiencing a DLT, the Bayesian model will be updated with the newly accumulated data. The SC will then determine the dose regimen for the next dose-level cohort, based on the available toxicity information (including DLTs, AEs that are not DLTs, and AE information post-cycle 1), recommendations from the BLRM, and other data (e.g. anti-tumour activity, pharmacokinetics) if applicable. Details on the Bayesian design are provided in [Sections 7.1](#) and [Appendix 10.6](#).

The overdose risk will be calculated for each further dose combination, and patient enrolment into dose levels will be permitted to all dose combinations which fulfil the escalation with overdose control (EWOC) criterion. Based on the Bayesian model and the additional information as defined above, the SC will decide on the next dose level to be investigated. In the SC meeting, data for each patient in the current dose-level cohort will be described in detail, updated safety data on other ongoing patients, including data in later courses, will be discussed as well.

The SC must reach a consensus on whether to de-escalate, re-escalate and/or expand recruitment into particular cohorts, or to declare the MTD₁/RP2D₁. BI will prepare minutes from the SC meetings and circulate them to each Investigator.

To further assess the safety (e.g. specific suspected treatment-related adverse events) of xentuzumab in combination with abemaciclib, one or several doses that are considered acceptably safe, i.e. shown to be lower than or equal to any potential MTD, may be explored to determine the RP2D₁. Nevertheless, a minimum of 6 evaluable patients need to be treated at the MTD₁/RP2D₁ in the dose finding cohort A prior to starting part 2 (cohorts B, C, D and E) and any dose declared as MTD₁/RP2D₁ by the SC needs to fulfil the escalation with overdose control (EWOC) criteria.

The SC may recommend stopping the dose finding cohort A after the criterion for MTD ([Section 7.1](#)) is fulfilled. Further patients may be included to confirm the MTD₁/RP2D₁ estimate, i.e. to confirm that the EWOC criterion is still fulfilled prior to the start of part 2 (cohorts B, C, D and E).

4.1.2.2 Part 2

The decision on dose escalation/de-escalation, MTD (or Biological Relevant Dose) and RP2D will be determined in discussion with at least BI Trial Clinical Monitor, BI project physician (TMM) and Coordinating Investigator and taking into account patients' safety. This decision will be documented.

Dose finding cohorts B, C and D (dose finding):

For each cohort, starting dose of xentuzumab and abemaciclib will be the RP2D₁ determined in cohort A, even if RP2D₁ equals the highest dose levels planned (see [Table 4.1.2.1: 1](#)). This is because the maximum dose of abemaciclib to be explored in triple combination cohorts is 150mg b.i.d. In that case, the starting dose would then be 1000 mg weekly xentuzumab plus 150 mg / 12h abemaciclib.

In the three cohorts, patients will receive the dose of background hormonal therapy as defined in [Tables 4.1.1: 3](#) to [4.1.1: 5](#) (i.e. letrozole in cohort B, anastrozole in Cohort C and fulvestrant in cohort D).

Dose escalation/de-escalation of xentuzumab and abemaciclib will be conducted as described in [Section 4.1.2.1](#) for cohort A using a BLRM with a fixed dose of the background hormonal therapy.

Expansion cohort E:

Patients will be treated at the RP2D₁ determined in Cohort A.

4.1.2.3 Part 3

Cohorts F, D1 and D2

For Cohort F and Cohorts D1 and D2 patients will be treated at the RP2D₄ of abemaciclib and xentuzumab and fulvestrant triplet as determined in Cohort D (dose finding).

4.1.3 Method of assigning patients to treatment groups

For the dose finding cohorts, the treatment slots are assigned by the BI Clinical Monitor (CM) in close communication (email/phone/fax) with the recruiting sites and IRT system and will be assigned on a competitive basis. After the BI Clinical Monitor has been notified by a site about a potential patient, the slot will be reserved to this site for a period of time (approximately a week) until patient signs ICF, otherwise the slot will be opened up again for all recruiting sites. If more than one site notifies potential patients and there are no slots for all proposed candidates, BI Clinical Monitor will allocate the slot prioritizing by planned visits calendar, balanced number of patients per site and other parameters as applicable.

Patients that meet the eligibility criteria and who have given their written informed consent may not be entered into the study depending on the cohort which is being explored at that particular time (for example, but not restricted to, the dose finding cohort A). This needs to be discussed and agreed with BI Trial Team.

Prior to inclusion of a new patient, once the slot has been confirmed, the investigator should also confirm the respective dose with the BI clinical monitor.

4.1.4 Drug assignment and administration of doses for each patient

The treatment medication assignment for xentuzumab and abemaciclib will be managed through IRT system. The treatment medication assignment for anastrozole, letrozole and fulvestrant will be managed through IRT system in certain countries only.

In addition, patient's screening, run-in, all drug dispensation visits and EOTV will be collected in the IRT system.

4.1.4.1 Initial study drug assignment and administration

General information that applies in this study regardless of IRT is described in below sections of individual study drug. The medication kit as well as the treatment will be assigned with the support from IRT.

Before entering patients at the next dose level of the dose finding cohorts, it will be ensured that all patients at the current ongoing dose level have completed at least one course of treatment.

Xentuzumab

Patients will start treatment with their assigned dose tier (see [Section 4.1.2](#)) or RP2D of xentuzumab from course 1 day 1. Xentuzumab will be administered at the investigator site intravenously over one hour with a constant infusion rate on the treatment day as specified in the [Flow Chart](#). If scheduled infusion of xentuzumab is not performed within the time window, this treatment will be skipped and will not be made up. Subsequent visits should follow the original visit date schedule. Mannitol is used in the formulation of xentuzumab, so infusion duration of less than one hour must be avoided. The infusion time may be extended to over one hour and up to a maximum of three hours in cases of CTCAE grade ≥ 2 infusion reactions. In case of a delay or an interruption of infusion, the reason and the exact time of deviation must be recorded in the specific eCRF. The accuracy of this information is crucial for the proper evaluation and appraisal of the pharmacokinetics – in the relevant cohorts – and other data.

Detailed information of dispensation, preparation, and handling of xentuzumab will be described in ISF.

Abemaciclib

Abemaciclib will be taken orally every 12 (± 2) hours on days 1 through 28 of a 28-day cycle for a total of 56 doses per cycle. During all cycles, abemaciclib should be taken at approximately the same times each day. If a patient misses or vomits a dose, that dose should be omitted.

No more than 56 doses of abemaciclib should be dispensed for each 28-day cycle.

Abemaciclib dose omissions will be evaluated on a case by case basis and patients may be replaced if dose omissions occur within MTD period of a dose finding cohort or if the number of dose omissions makes the patient non evaluable regardless of the cohort.

4.1.4.2 Temporary treatment interruption and dose reduction

DLT, or those AEs requiring dose adjustment as indicated on the label, should be managed by treatment interruptions and subsequent dose reductions of the presumed causal study drug(s) according to the schedule described in [Table 4.1.4.2: 1](#). Please also refer to [Section 4.4](#) for additional recommendations.

In case of an intolerable adverse event which is suspected to be related to either xentuzumab or abemaciclib in the opinion of investigator, the treatment can be interrupted with subsequent dose reduction for the suspected agent(s) according to [Tables 4.1.4.2: 1](#) (xentuzumab) and [4.1.4.2: 2](#) (abemaciclib).

In the case of DLT with suspected overlapping toxicities where assigning relatedness to one study drug or the other is difficult, or considered related to both xentuzumab and abemaciclib the dosing with both study drugs should be held until the adequate resolution of AE (CTCAE grade ≤ 1). Treatment should then be resumed and/or dose reduced as shown in [Table 4.1.4.2: 1](#) for xentuzumab and in [Table 4.1.4.2: 2](#) for abemaciclib.

Recurrent in the context of dose interruptions and delays refers to the same event and severity occurring within 8 weeks (as measured from the stop date of the first event). This does not

include events in the same class (for example, neutropenia followed by anemia 1 month later).

Further to these recommendations, in Part 1, Cohort A, both xentuzumab and abemaciclib must be paused when a DLT occurs during the first treatment course.

The treatment should be paused until patient has recovered from the DLT to grade ≤ 1 or baseline. Baseline is defined as the CTCAE grade at the start of treatment. For patients who develop DLT, treatment may be resumed at reduced dose according to dose reduction scheme of the patient's starting dosage. If a patient has not recovered to Grade ≤ 1 or baseline within 28 days, study treatment must be permanently discontinued. In the event that the patient is deriving obvious clinical benefit according to the investigator's judgement, further treatment with study drug(s) will be decided in agreement between the sponsor and the investigator.

If one or more of the study drugs is permanently discontinued, the patient can remain on either abemaciclib or xentuzumab or endocrine therapy only.

Dose reductions will apply to individual patients only. Doses of xentuzumab and/or abemaciclib can be reduced independent of each other. Once the treatment dose of xentuzumab is reduced for a particular patient, it should not be increased back to the previous dose.

Abemaciclib dose adjustments are allowed within a cycle and between cycles. Abemaciclib must be reduced sequentially by one dose level. For further instructions as regards dose adjustments of abemaciclib, please refer to [Section 4.2.2](#).

For patients requiring dose reduction(s) of abemaciclib, any re-escalation to a prior dose level is permitted only after discussion and agreement with the sponsor. After re-escalation, subsequent dose adjustments should be based on the dose of abemaciclib that the patient is currently receiving.

Table 4.1.4.2: 1 Individual dose reductions schedule

Xentuzumab mg/weekly		Abemaciclib mg/12 h	
Current dose is 1000	Dose reduce to 750	Current dose is 150	Dose reduce to 100
Current dose is 750	Dose reduce to 500	Current dose is 100	Dose reduce to 50
Current dose is 500	No further dose reductions allowed.	Current dose is 50	No further dose reductions allowed.

No dose reduction is allowed below 500 mg/weekly for xentuzumab or 50 mg b.i.d. for abemaciclib.

Alternative dose modification scheme can only be considered after discussion and agreement between the investigator and the BI clinical monitor.

In the event of any unrelated AEs, the study drug(s) may be interrupted for up to 28 days, but no dose reduction should occur. Otherwise, the decision to continue with the study treatment will be made by the BI Clinical Monitor in agreement with the investigator.

Proprietary confidential information © 2024 Boehringer Ingelheim International GmbH or one or more of its affiliated companies

Table 4.1.4.2: 2 Dose Adjustments and Delays for Toxicity Possibly Related to Abemaciclib*

Toxicity Type	Toxicity Profile and Severity	Dose Suspension	Dose Reduction
Hematologic Toxicity	Grade 3	Dose MUST be suspended until toxicity resolves to at least Grade 2.	Dose MAY be reduced by 1 dose level - investigator's discretion.
Hematologic Toxicity	Recurrent Grade 3 ¹	Dose MUST be suspended until toxicity resolves to at least Grade 2.	Dose MUST be reduced by 1 dose level.
Hematologic Toxicity	Grade 4	Dose MUST be suspended until toxicity resolves to at least Grade 2.	Dose MUST be reduced by 1 dose level.
Hematologic toxicity: If patient requires administration of blood cell growth factors.	Regardless of severity. (Use of growth factors according to ASCO Guidelines)	Dose MUST be suspended for at least 48 hours after the last dose of blood cell growth factors was administered and until toxicity resolves to at least Grade 2.	Dose MUST be reduced by 1 dose level unless already performed for incidence of toxicity that led to the use of growth factor.
Nonhematologic Toxicity ² (except diarrhoea, ALT increase and ILD/pneumonitis)	Persistent or recurrent ³ Grade 2 that does not resolve with maximal supportive measures within 7 days to baseline or Grade 1	Dose MUST be suspended until toxicity resolves to either baseline or Grade 1.	Dose MUST be reduced by 1 dose level.
ILD/pneumonitis ⁵	Grade 2 that persists or recurs despite maximal supportive measures and does not return to baseline or Grade 1 within 7 days	Suspend dose until toxicity resolves to baseline or \leq Grade 1.	Dose MUST be reduced by 1 dose level.
ILD/pneumonitis	Grade 3 and 4	Dose MUST be discontinued	NA
Nonhematologic Toxicity	Grade 3 or 4	Dose MUST be suspended until toxicity resolves to either baseline or Grade 1.	Dose MUST be reduced by 1 dose level.
Diarrhoea	Grade 2 that does not resolve within 24 hours to at least Grade 1	Dose MUST be suspended until toxicity resolves to at least Grade 1.	Dose MAY be reduced by 1 dose level - investigator's discretion.

Table 4.1.4.2: 2 (cont.) Dose Adjustments and Delays for Toxicity Possibly Related to Abemaciclib*

Toxicity Type	Toxicity Profile and Severity	Dose Suspension	Dose Reduction
Diarrhoea	Requires hospitalization or Grade 3 or 4	Dose MUST be suspended until toxicity resolves to at least Grade 1.	Dose MUST be reduced by 1 dose level.
Diarrhoea	Grade 2 that persists or recurs after resuming the same dose despite maximal supportive measures	Dose MUST be suspended until toxicity resolves to at least Grade 1.	Dose MUST be reduced by 1 dose level.
Increased ALT	Persistent or Recurrent ³ Grade 2 ($>3.0\text{-}5.0\times\text{ULN}$), or Grade 3 ($>5.0\text{-}20.0\times\text{ULN}$) ⁴	Dose MUST be suspended until toxicity resolves to either baseline or Grade 1.	Dose MUST be reduced by 1 dose level.
Increased ALT with increased total bilirubin, in the absence of cholestasis	Grade 3 ($>5.0\times\text{ULN}$) with total bilirubin $>2\times\text{ULN}$	Abemaciclib MUST be discontinued	NA
Increased ALT	Grade 4 ($>20.0\times\text{ULN}$)	Abemaciclib MUST be discontinued	NA

*In case that the Toxicity Profile and Severity qualifies for DLT according to [Section 5.3.7](#), dose suspension and dose reduction will be followed according to the DLT management instructions

¹ Recurrent toxicity refers to the same event occurring within the next 8 weeks (as measured from the stop date of the preceding event). As a general guidance, based on the risk/benefit balance assessment per the investigator, for a patient who experiences a new episode of Grade 3 hematological toxicity after more than 8 weeks following the last episode of same Grade 3 hematological toxicity, the investigator may consider resuming the patient on the same drug dose should the patient satisfy the following conditions:

- shows stable hematological counts (Grade ≤ 2) during that timeframe
- has absence of any signs or risk of infection
- is benefiting from study treatment

² Additional guidance for renal monitoring is in [Section 4.4.1](#)

³ Determination of persistent events will be at the discretion of the investigator. Recurrent toxicity refers to the same event occurring within the next 8 weeks (as measured from the stop date of the preceding event).

⁴ Grade 3 ALT increased is a trigger for additional assessments and possibly hepatic monitoring. See [Section 4.4.4](#) for additional guidance for hepatic monitoring

⁵ For Japan only: refer to local amendment in Japan for ILD guidance

Abbreviation: ASCO = American Society of Clinical Oncology.

Note: MAY = per the investigator's clinical judgment; MUST = mandatory.

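### The footnote to Table 4.1.4.2:2 sends DLTs to rules that permit restart, without saying that the table's mandatory abemaciclib stops for severe liver toxicity take precedence

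*Protocol*

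**What the plan says.** Protocol Table 4.1.4.2:2 sets dose adjustments for toxicity possibly related to abemaciclib. Three of its rows order a stop and show dose reduction as not applicable: Grade 3 or 4 ILD/pneumonitis, Grade 4 ALT, and the row headed "Increased ALT with increased total bilirubin, in the absence of cholestasis". For both liver rows the entry is "Abemaciclib MUST be discontinued", and the note under the table explains that "MUST = mandatory". These entries stand in the column headed "Dose Suspension".

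The table's title carries an asterisk. Its footnote opens "In case that the Toxicity Profile and Severity qualifies for DLT according to" Section 5.3.7, and continues that "dose suspension and dose reduction will be followed according to the DLT management instructions".

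The DLT instructions are in the text of Section 4.1.4.2. A DLT leads to interruption and "subsequent dose reductions of the presumed causal study drug(s) according to the schedule described in" Table 4.1.4.2:1, with a further pointer to Section 4.4. For a DLT related to both drugs, or hard to attribute, both are held until resolution: "Treatment should then be resumed and/or dose reduced as shown in" Table 4.1.4.2:1 for xentuzumab and Table 4.1.4.2:2 for abemaciclib. A later paragraph pauses treatment until Grade 1 or lower, or baseline, and then permits resumption at a reduced dose. Non-recovery within 28 days means a permanent stop, unless sponsor and investigator agree otherwise for a patient with obvious clinical benefit.

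**The concern.** The same liver event can fall under two instructions. One stops abemaciclib for good. The other pauses it and allows it back at a lower dose. A site needs to know which governs, and the protocol does not say.

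The 28-day rule does not close the gap. It catches the patient who fails to recover, whereas restart is offered to the patient who does recover. At stake is re-exposure to abemaciclib after drug-related liver toxicity that the table treats as a permanent stop. The table is still in use: Section 3.3.4.2 lets patients who come off xentuzumab continue on abemaciclib and fulvestrant.

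**Working it through.** There is no plan figure to reproduce. The check has three parts.

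**1. Do the stop-row events qualify as DLTs?**

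Inputs:
- ALT criterion for a DLT (5.3.7): above 5×ULN if baseline is at or below ULN; above baseline + 4×ULN if baseline is raised. The event must be at least possibly related to study drug and not clearly attributable to progression or another identified cause.
- Entry ceiling for ALT (3.3.3, exclusion 14): 2.5×ULN, or 5×ULN with liver metastases.
- Assumption: ALT at treatment start is within the entry ceiling.

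Highest possible ALT threshold for a DLT:
- without liver metastases: 2.5 + 4 = 6.5×ULN
- with liver metastases: 5 + 4 = 9×ULN

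Grade 4 ALT row (above 20×ULN): 20 > 9, so every related event meets the criterion.

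ALT and bilirubin row (ALT above 5×ULN): always met when baseline ALT is at or below ULN. At a raised baseline *b* (in ×ULN) the limit is *b* + 4, so ALT values from 5 to *b* + 4 fall in the stop row but below the ALT limit. The band has width (*b* + 4) − 5 = *b* − 1.

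| Baseline *b* (×ULN) | ALT limit for a DLT | Band below the limit | Width |
|---|---|---|---|
| 1.5 | 5.5 | 5 to 5.5 | 0.5 |
| 2.0 | 6.0 | 5 to 6 | 1.0 |
| 2.5 | 6.5 | 5 to 6.5 | 1.5 |
| 5 (liver metastases) | 9.0 | 5 to 9 | 4.0 |

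Events in the band can still be DLTs through another 5.3.7 criterion, such as the AST limit, a 2-week interruption or investigator judgement. Grade 3 or 4 pneumonitis always meets its own DLT criterion of Grade 3 or above.

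**2. Does the footnote reach the stop rows?**

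It hangs on the title, so it covers the whole table. It uses the table's own column names, the stop entries sit under one of those columns, and no row is excepted. Elsewhere in the table it changes the rule: haematologic rows allow restart at Grade 2, whereas the DLT paragraph requires Grade 1 or baseline.

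**3. Do the cross-references settle precedence?**

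- DLT blamed on one drug: the text points to Table 4.1.4.2:1, which lists dose steps and has no stop rows, and to Section 4.4. For the liver, 4.4.4 speaks of possible dose modification and refers to Table 4.1.4.2:2. That table's footnote returns DLTs to the DLT instructions.
- DLT related to both drugs or hard to attribute: the text points abemaciclib to Table 4.1.4.2:2, with the same footnote and the same return.

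Both routes are circular. Outside the table, the hepatic-injury text in 5.3.6.1 and Appendix 10.5 covers reporting, work-up and follow-up, and neither orders a stop. Severe ILD differs, because 4.4.6 independently says to discontinue abemaciclib.

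**The case against.** The strongest reply is that the rules do not truly conflict. The table distinguishes suspending, reducing and discontinuing, and the footnote redirects only the first two. Discontinuation is not named, the stop entries are expressly mandatory, and restart under the DLT text is only permitted. A site that stops abemaciclib complies with every sentence. Moreover, where the footnote visibly changes the haematologic rows it tightens them, so it would be odd for it to loosen the strictest rows.

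This stands as evidence of intent, and it makes the surviving-stop reading a fair one. It does not settle the text. The note on MUST defines a word without ranking a row against the footnote, and a site that restarted could point to a footnote that excepts no row.

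The objection also lists safeguards: hepatic injury meeting the alert criteria is reported within 24 hours (5.3.6.1, 5.3.6.2), Appendix 10.5 requires a work-up, and 3.3.4.1 allows withdrawal for medical reasons. These lower the risk, but none states the dosing rule.

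A reader might infer that no liver stop exists anywhere in the trial's materials. The documents do not show that. The DILI checklist in the site file and the abemaciclib label, to which the protocol refers, were not available for this review.

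A reader might also size the problem by planned enrolment: 12 in Cohort A, 48 in dose finding or 148 in all. Those are recruitment targets, not patients still treated under this text. The reach of the DLT rules is itself unclear, since the restart sentence follows one about Cohort A in the first course. The SAP introduction also reports that safety analyses after the dose-finding cohorts were already performed.

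**Conclusion.** The point holds as an unresolved collision between a stop rule and a restart rule, and it matters most for the two liver rows. Read literally, the protocol lets a site resume abemaciclib at a reduced dose after related Grade 4 ALT, or after a DLT-level ALT rise with raised bilirubin, once the event has resolved within 28 days.

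A stronger reading would be that the protocol cancels the mandatory stops or instructs sites to restart. The text supports neither: restart is an option and discontinuation is never expressly overridden.

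The overlap result rests on ALT at treatment start being within the entry limits and on the event being at least possibly drug-related. The absence of another liver-specific stop is established only for the protocol and SAP. The number of patients or events affected is not established. Severity: a minor safety clarification of conflicting rules.

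**What to change.** Add to the asterisk footnote, and mirror in the DLT paragraph of 4.1.4.2: *Rows stating that abemaciclib (or dose) MUST be discontinued take precedence over the DLT management instructions; abemaciclib must not be resumed after these events.* The words in brackets are needed because the ILD row is phrased in terms of the dose.

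The cost is one sentence in two places, by amendment with a letter to sites. It adds no procedures or patients, and 4.1.4.2 already lets a patient stay on the remaining study drugs when one is stopped.

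Optional at the same time: repeat the two liver stops in 4.4.4, state whether DLT management applies in the expansion cohorts, and check the Japanese local amendment on ILD, not seen here, for the same ambiguity.
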